### 4.2.3 Exploratory Outcome Measures

We will examine potential mediators of change in our primary outcomes during the 3- month treatment period, decreased avoidance of life activities (BADS [Behavioral Activation for Depression Scale]), and decreased pain anxiety or fear of pain (PASS [Pain Anxiety Symptoms Scale]).

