## 15.3 Statistical Methods

We will present descriptive statistics. Random effects logistic regression will be used to determine if treatment condition, demographic characteristics, or baseline outcome measures predict study attrition. Any variables that significantly ( $p < .10$ ) predict study attrition will be included in multiple imputation models and as covariates in multivariate models testing the effects of intervention. Graphical methods will be used to evaluate the distributions of outcome variables, examine model residuals, describe change in outcomes over time, and guide the specification generalized linear mixed models testing intervention effects. A 2-tailed probability of Type I error  $< 0.05$  will be used for all null hypothesis tests. Missing data due to participant attrition and item non-response is inevitable. We will conduct intent-to-treat analysis using multiple imputation by chained equation (MICE) to generate fully populated data sets [20]. More specifically we will use the mi impute and mi estimate facilities in Stata 17 to generate and analyze the fully populated data files [21]. The number of imputed data sets will be determined by using the how many imputations procedure [22]. MICE is a flexible tool that allows imputing values for outcomes with a range of distributions (e.g., continuous, dichotomous, count, etc.). MICE assume data are missing at random (MAR) (e.g., missing is random conditional on variables in the imputation model). Variables used in the imputation models will include treatment assignment, all observed instances of the outcome being imputed, and any additional baseline variables found to significantly ( $p < .10$ ) predict subject attrition using mixed-effects logistic regression. Including baseline predictors of attrition supports the MAR assumption.

The BPI, the VAS pain severity scales (worst and average in last week), and the PHQ-9 will be administered at baseline and at all follow-up assessments. The effect of intervention on pain interference (BPI-I), pain severity, and depressive symptoms during the 3-month treatment phase will be evaluated in a generalized linear mixed model framework using the fully populated data sets generated by MICE. Models will include baseline pain and PHQ-9 depression measures as covariates. All available panel data will be included in the model to support the efficiency of estimation. Time specific estimates

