of treatment effects (e.g., the effect of treatment at 3-months) can be obtained by including the treatment by categorical (indicator variables) time interaction term. We plan to use the contrast and mimrgns post-estimation commands in Stata to recover relevant parameter estimates and test statistics. More specifically, a Wald  $\chi^2$ -test will be used to test the simple main effect of treatment at end of treatment. Additionally, we will generate graphs plotting the estimated average marginal means to facilitate substantive interpretation of results. Parallel methods will be used to evaluate the sustained effect of treatment post end-of-treatment (4-, 6-, 9-, and 12- months). Wald  $\chi^2$ -tests will again be used to test the simple main effects of treatment at post end-of-treatment assessments to determine if intervention effects are sustained over time.

The Cox proportional hazards model will be used to test the hypothesis that participants randomized to TOPPS will have higher buprenorphine treatment retention than persons randomized to HE. The outcome will be operationalized as self-reported continuous treatment since the prior interview at the time point assessed.

We will use Mplus 7 [23] to specify and estimate structural equation models (SEM) testing the hypothesis that decreased avoidance, and fear of pain mediate the relationship between intervention and pain interference and severity.

Additional baseline covariates will include ratings of pain severity, pain interference, and depression. As recommended by MacKinnon et al. [24], the statistical significance of the indirect effect will be assessed using bias-corrected bootstrapped standard errors. Significant indirect effects are consistent with the hypothesis that change in the purported mechanisms mediates the effect of intervention on outcome.

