## 18 Appendix

### Schedule of Events

**Table 1. Schedule of Study Measures**

Measure	Description	Baseline	Sessions	Follow-Up Assessment (Months)							
				1	2	3	4	6	9	12	
Sociodemographics Baseline	Demographic questions, including age and incarceration history	X									
Sociodemographics Follow-up	Demographic questions,	X		X	X	X	X	X	X	X	

	including places slept									
PHQ-9 	Measure of severity of depression	X	X	X	X	X	X	X	X	X
BPI 	Ratings of pain severity and interference	X	X	X	X	X	X	x	X	X
Pain Experiences 	Time ratings of least severe pain	X		X	X	X	X	X	X	X
BADS 	Measure of behavioral activation of depression	X		X	X	X	X	X	X	X
Buprenorphine and Pain - Baseline	Measures of how buprenorphine helps with pain	X								
GAD-7 	Measure of severity of anxiety	X		X	X	X	X	X	X	X
TSR – Baseline 	Compiling a list of medical appointments in the past 3 months	X								
TSR- Follow-Up 	Compiling a list of medical appointments since last follow-up			X	X	X	X	X	X	X
TRAQ 	Compiling a list of current medications	X		X	X	X	X	X	X	X
Knowledge Questionnaire	Assess patient knowledge of opioids	X								
Pain Treatment Questionnaire 	Endorsements of pain treatments	X		X	X	X	X	X	X	X

	used and ranking of their helpfulness									
IPAQ 	Measure of physical activities in the past 7 days	X		X	X	X	X	X	X	X
CPAQ 	Assess acceptance of chronic pain	X		X	X	X	X	X	X	X
PASS 	Assess anxiety around pain	X		X	X	X	X	X	X	X
PROMIS Global Health 	Assess general domains of health and functions	X		X	X	X	X	X	X	X
ASI – Baseline 	Compile lifetime use of drugs and in the last 30 days	X								
ASI – Follow-up 	Compile use of drugs in the last 30 days			X	X	X	X	X	X	X
Nicotine 	Determine cigarette use and how often	X								
DIS 	Assessing Pain sensitivity	X				X		X		X
Perceived Control Scale 	Assessing sense of agency	X			X			X		X
CPV-I 	Determine values and success living according to those values	X		X	X	X	X	X	X	X
Experience of Discrimination 	Determine history of discrimination based on identity	X								

Buprenorphine and Pain – Follow-up	Assessing buprenorphine effectiveness with pain			X	X	X	X	X	X	X	X

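### The mediation model does not state that each mediator's own baseline (BADS, PASS) is a covariate, which leaves the mediator-to-outcome path open to confounding

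*Combined protocol and SAP*

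**What the plan says.** Section 15.3 plans structural equation models "testing the hypothesis that decreased avoidance, and fear of pain mediate the relationship between intervention and pain interference and severity". On adjustment it says: "Additional baseline covariates will include ratings of pain severity, pain interference, and depression". It then interprets the result in terms of change: "Significant indirect effects are consistent with the hypothesis that change in the purported mechanisms mediates the effect of intervention on outcome".

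Section 4.2.3 names the instruments, BADS for avoidance and PASS for pain anxiety or fear of pain, and places this analysis among the exploratory outcomes. Table 1 schedules BADS ("Measure of behavioral activation of depression") and PASS ("Assess anxiety around pain") at baseline and at months 1, 2, 3, 4, 6, 9 and 12.

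No passage names baseline BADS or PASS as a covariate. The one rule that adds covariates from the data is the attrition screen in section 15.3, which asks "if treatment condition, demographic characteristics, or baseline outcome measures predict study attrition". Mediators are not on that list.

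**The concern.** The hypotheses are about decreased avoidance and decreased fear. A participant's follow-up score reflects the starting level as well as any change, so the model needs a stated way of handling that level.

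Randomisation makes the treatment-to-mediator path a fair comparison. It does nothing for the mediator-to-outcome path. Someone who starts more avoidant will tend to be more avoidant at follow-up, and may also have worse pain interference for reasons unrelated to the trial. Unless the starting level is in the outcome equation, part of that stable difference between people is credited to the mediator and then multiplied into the indirect effect. At stake is whether the trial can say that TOPPS works through reduced avoidance or fear.

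**Working it through.** **The plan's own figure.** The documents give no power or sample-size figure for mediation. The only calculation is for Aim 1: 2 × (1.960 + 0.842)² / 0.4² = 98.1, rounded up to the stated 99 per arm. It reproduces but does not bear on this model.

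**Inputs.** From the documents: 163 randomised (section 2), 1:1 allocation (section 5), two-sided 0.05 (section 15.3). Assumed, since the documents give none of these:
- One mediator, coded so that higher is better; no missing data.
- Treatment-to-mediator effect a = 0.4 SD; mediator-to-outcome effect b = 0.3; true indirect effect a × b = 0.12.
- Baseline-to-follow-up mediator coefficient s = 0.5 or 0.7.
- One baseline pain covariate, correlated 0.4 with the baseline mediator and already in the model.
- Outcome residual SD 0.75.
- Direct effect d of the baseline mediator on the outcome, from −0.15 to 0.30.

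**Bias if the baseline mediator is left out.** Given treatment and baseline pain, the baseline mediator has variance 1 − 0.4² = 0.84, and the follow-up mediator has variance 1 − 0.16s². The mediator-to-outcome coefficient becomes b + d × k, where k = 0.84s / (1 − 0.16s²).
- s = 0.5: k = 0.42 / 0.96 = 0.4375
- s = 0.7: k = 0.588 / 0.9216 = 0.638

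The expected indirect effect is 0.4 × (0.3 + d × k). Simulated means (2,000 trials per setting, N = 163) are in brackets.

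| d | s = 0.5 | s = 0.7 |
|---|---|---|
| −0.15 | 0.094 (0.095) | 0.082 (0.081) |
| 0 | 0.120 (0.119) | 0.120 (0.122) |
| 0.15 | 0.146 (0.147) | 0.158 (0.157) |
| 0.30 | 0.173 (0.174) | 0.197 (0.195) |

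At d = 0.15 the simulated excess is 0.1465 / 0.12 − 1 = 22% and 0.1568 / 0.12 − 1 = 31%. With the baseline mediator in both equations, the simulated mean stayed at 0.118–0.123 in every row. A separate run at N = 130 (about 80% of 163) gave 0.148–0.157 for d = 0.15.

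**False positives when b = 0.** This used joint significance of both paths as a stand-in for the planned bootstrap, with a still 0.4 and N = 163. For d = 0.15–0.30, the rate without the baseline mediator was 0.13–0.40 (s = 0.5) and 0.26–0.64 (s = 0.7). With it, the rate was about 0.04–0.05. At N = 130 the ranges were 0.10–0.48 and 0.03–0.04.

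**Change score instead.** Using follow-up minus baseline as the mediator, at s = 0.5 and d = 0.15, the coefficient is 0.3 × (0.54 / 0.96) − 0.15 × (0.42 / 0.96) = 0.103. The indirect effect is then 0.4 × 0.103 = 0.041 (simulated 0.042), about a third of the truth.

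**Power.** Treatment-to-mediator path, SMD 0.4, 81.5 per arm: power = Φ(0.4 × √(81.5/2) / √(1 − r²) − 1.96). Here r is the correlation of baseline with follow-up mediator beyond the covariates already listed. This gives 0.72 at r = 0, 0.84 at r = 0.5 and 0.95 at r = 0.7.

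On the mediator-to-outcome path the adjustment removes mediator variance, so the standard error rises. At s = 0.7 and d = 0 it goes from 0.75 / √(163 × 0.9216) = 0.061 to 0.75 / √(163 × 0.51) = 0.082. The net effect on the joint test (simulated, N = 163, d = 0) depends on which path is weaker:

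| a, b | s | Without | With |
|---|---|---|---|
| 0.4, 0.3 | 0.5 | 0.73 | 0.82 |
| 0.4, 0.3 | 0.7 | 0.74 | 0.88 |
| 0.6, 0.15 | 0.5 | 0.67 | 0.58 |
| 0.6, 0.15 | 0.7 | 0.66 | 0.44 |

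**The case against.** The strongest reply is that the plan is silent and excludes nothing. The covariate sentence opens with *Additional* and never says additional to what. The covariates it names are pain and depression, which fits a model that already handles each mediator's baseline. The section also speaks of change in the mechanisms. This stands as far as it goes: a reader might infer that the model leaves out baseline BADS and PASS, and the documents do not support that. Nor do they put these measures in, and a programmer could not build the model from the hint. The word *change* does not settle it either, because a change score and a baseline-adjusted mediator give different answers (0.04 against 0.12 above).

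A reader might also infer that the omission costs power. It does so only in some settings: where the mediator-to-outcome path is the weak one, adding the baseline mediator lowers power. The documents give no values that would say which case applies.

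A third inference is that the bias must be upward. It can be upward, downward or nil, depending on d. Stronger overlap between the listed covariates and the baseline mediator also shrinks it. With a correlation of 0.7 instead of 0.4, the excess at d = 0.15 falls to about 14–23%.

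Finally, the analysis is exploratory, and section 15.3 claims only consistency with the mediation hypothesis. That limits the priority but does not make the specification adequate.

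**Conclusion.** The concern holds as a gap in specification that affects the result. Section 15.3 does not state that each mediator is adjusted for its own baseline, and the readings it permits lead to materially different indirect effects. Of the three models compared, only the one with the baseline mediator in both equations recovered the true value wherever they were compared.

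The sizes are illustrative, because every mediation input is assumed. The 20–30% overstatement belongs to d = 0.15 in the same direction as b; a larger d gives more. The inflated false-positive rate needs both a real treatment effect on the mediator and a direct effect of the baseline mediator on the outcome. The simulations used one mediator, complete data and a joint-significance test, not the full model with bootstrapped standard errors.

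Adjustment sharpens the treatment-to-mediator path whenever the baseline predicts follow-up. No general power gain for the indirect effect is claimed. Primary and secondary results are untouched. Priority: minor to moderate.

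**What to change.** Replace the covariate sentence in section 15.3 with wording such as: *Each follow-up mediator will be adjusted for its own baseline score (BADS for avoidance, PASS for fear of pain) in both the mediator equation and the outcome equation, together with baseline pain severity, pain interference and depression.* Settle this before the mediation results are seen.

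The cost is a change of wording and two more covariates, both already collected. The one statistical downside is possibly lower power for the indirect effect if the mediator-to-outcome path is weak. That is a fair price, since part of the power of the unadjusted model can come from confounding. The adjustment removes confounding by the starting level of the mediator only; other common causes of mediator and outcome remain, so the cautious wording of the interpretation should stay.

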## 16 Ethics/Protection of Human Subjects

This study is to be conducted according to applicable US federal regulations and institutional policies (which are based in federal regulations, guidance, and ICH (International Council for Harmonization) Good Clinical Practice guidelines).

This protocol and any amendments will be submitted to the Boston Medical Center and Boston University Medical Campus IRB / Name of IRB of record for formal approval of the study conduct. The decision of the IRB concerning the conduct of the study will be made in writing to the investigator. A copy of the initial IRB approval letter will be provided to the sponsor before commencement of this study.

All subjects for this study will be provided a consent form describing this study and providing sufficient information for subjects to make an informed decision about their participation in this study. The consent form will be submitted with the protocol for review and approval by the IRB. The consent of a subject, using the IRB-approved consent form, must be obtained before that subject is submitted to any study procedure. Consent will be documented as required by the IRB.

## 18 Appendix

### Schedule of Events

**Table 1. Schedule of Study Measures**

Measure	Description	Baseline	Sessions	Follow-Up Assessment (Months)							
				1	2	3	4	6	9	12	
Sociodemographics Baseline	Demographic questions, including age and incarceration history	X									
Sociodemographics Follow-up	Demographic questions,	X		X	X	X	X	X	X	X	

	including places slept									
PHQ-9 	Measure of severity of depression	X	X	X	X	X	X	X	X	X
BPI 	Ratings of pain severity and interference	X	X	X	X	X	X	x	X	X
Pain Experiences 	Time ratings of least severe pain	X		X	X	X	X	X	X	X
BADS 	Measure of behavioral activation of depression	X		X	X	X	X	X	X	X
Buprenorphine and Pain - Baseline	Measures of how buprenorphine helps with pain	X								
GAD-7 	Measure of severity of anxiety	X		X	X	X	X	X	X	X
TSR – Baseline 	Compiling a list of medical appointments in the past 3 months	X								
TSR- Follow-Up 	Compiling a list of medical appointments since last follow-up			X	X	X	X	X	X	X
TRAQ 	Compiling a list of current medications	X		X	X	X	X	X	X	X
Knowledge Questionnaire	Assess patient knowledge of opioids	X								
Pain Treatment Questionnaire 	Endorsements of pain treatments	X		X	X	X	X	X	X	X

	used and ranking of their helpfulness									
IPAQ 	Measure of physical activities in the past 7 days	X		X	X	X	X	X	X	X
CPAQ 	Assess acceptance of chronic pain	X		X	X	X	X	X	X	X
PASS 	Assess anxiety around pain	X		X	X	X	X	X	X	X
PROMIS Global Health 	Assess general domains of health and functions	X		X	X	X	X	X	X	X
ASI – Baseline 	Compile lifetime use of drugs and in the last 30 days	X								
ASI – Follow-up 	Compile use of drugs in the last 30 days			X	X	X	X	X	X	X
Nicotine 	Determine cigarette use and how often	X								
DIS 	Assessing Pain sensitivity	X				X		X		X
Perceived Control Scale 	Assessing sense of agency	X			X			X		X
CPV-I 	Determine values and success living according to those values	X		X	X	X	X	X	X	X
Experience of Discrimination 	Determine history of discrimination based on identity	X								

Buprenorphine and Pain – Follow-up	Assessing buprenorphine effectiveness with pain			X	X	X	X	X	X	X	X
Patient Global Impression of Change 	Assess impacts of study on their pain and sadness			X	X	X	X	X	X	X	X
CSQ-8 	Assess satisfaction with the intervention in general					X					
Patient Satisfaction 	Assess satisfaction with specific aspects of the intervention					X					
CEQ 	Assess effectiveness of intervention after Session 1	X									
Buprenorphine Adherence	Assess current use of buprenorphine		X								

Patient Health Questionnaire-9 and -2 (PHQ-9, -2), Brief Pain Inventory (BPI), Pain Experience, Behavioral Activation for Depression Scale (BADS), GAD-7 (General Anxiety Disorder-7), Treatment Services Review (TSR), Transition Readiness Assessment Questionnaire (TRAQ), Pain Treatment Questionnaire, International Physical Activity Questionnaire (IPAQ) , Chronic Pain Acceptance Questionnaire (CPAQ), Pain Anxiety Symptom Scale (PASS), Patient-Recorded Outcomes Measure Information System (PROMIS) Global Health, Addiction Severity Index (ASI), The Fagerström Test for Nicotine Dependence (Nicotine), Discomfort Intolerance Scale (DIS), Perceived Control Scale, Chronic Pain Value Inventory (CPV-I), Experience of Discrimination, Patient Global Impression of Change, Client Satisfaction Questionnaire-8 (CSQ-8), Patient Satisfaction, Credibility/Expectancy Questionnaire (CEQ)

**Table 2. Intervention Topics by Session**

Session Number	Week Number	Contents
Session 1	Week 1	• Introduction to TOPPS intervention

		
 
• Elicit history of participants' opioid use, recovery/buprenorphine treatment, pain, and depression, including an understanding of the participants' current and planned buprenorphine treatment and any medical treatment for pain and/or depression
 
• Explain the role of avoidance
 
• Values clarification
 
• Begin to explore participants' long-term goals
 
• Describe treatment and enhance motivation for the intervention
 
• Homework: participant is asked to continue identification of long-term goals and think about what is important in their life
 

Session 2	Week 2	
 
• Psychoeducation about core messages of TOPPS
 
• Pain and discomfort (e.g., sad feelings) are not dangerous in and of themselves
 
• Avoidance is a natural response to emotional and physical pain
 
• Pain and discomfort may be necessary to achieve important life goals
 
• Complete long-term goal setting.
 
• Teach SMART goals
 
• Set short-term, SMART goals corresponding to long- term goals, for the next 2 weeks.
 

Session 3	Week 4	
 
• Review core messages
 
• Review of short-term goals set at session 2 and any barriers to meeting these goals
 
• Discussion of time-based pacing
 
• Setting a short-term goal to apply pacing to physically active task (e.g., walking, cleaning)
 
• Setting of short-term goals corresponding to long-term goals for the following 2 weeks
 

Session 4	Week 6	
 
• Review core messages
 
• Discussion of short-term goals set at previous meeting, and barriers to meeting these goals
 
• Introduce concept of disease self-management and being an activated, informed patient. This includes discussions
 

		
of medication adherence, communication with provider, and making choices about one's own care.
 

• Setting of a goal that will help the participant to be more active in the management of their chronic conditions

• Setting of short-term goals corresponding to long-term goals for the following 2 weeks

Session 5	Week 8	

• Discussion of short-term goals set at previous meeting, and barriers to meeting these goals

• Setting of short-term goals corresponding to long-term goals for the following 2 weeks

• Identification of accomplishments made during the course of the intervention

• Planning for the participant to continue this work on their own

Session 6	Week 11	

• Discussion of short-term goals set at previous meeting, and barriers to meeting these goals

• Plan for how participant will continue to work towards long-term goals after end of therapy

